10.5.5 Adverse Event Classification

10.5.5.1 Relationship to Investigational Drug

The Investigator's assessment of causality must be provided for all TEAEs (serious and non-serious) (Table 11). An Investigator's causality assessment is the determination of whether there exists a reasonable possibility that the study drug caused or contributed to a TEAE.

These criteria, in addition to good clinical judgment, should be used as a guide for determining the causal assessment. If the event is believed to be unrelated to study drug administration, then an alternative explanation should be provided.

| Table 11: | Guidelines for Assessing Relationship of Event to Stud | ly Drug |
|-----------|--|---------|
|-----------|--|---------|

| Not related | The event is most likely produced by other factors such as the patient's clinical condition, intercurrent illness, or concomitant drugs, and does not follow a known response pattern to the study drug, or the temporal relationship of the event to study drug administration makes a causal relationship unlikely. |
|--------------------|---|
| Possibly related | The event follows a reasonable temporal sequence from the time of drug administration, and/or follows a known response pattern to the study drug, but is more likely produced by other factors such as the patient's clinical condition, intercurrent illness, or concomitant drugs. |
| Probably related | The event follows a reasonable temporal sequence from the time of drug administration, and/or follows a known response pattern to the study drug, but could be explained by other factors such as the patient's clinical condition, intercurrent illness, or concomitant drugs. |
| Definitely related | The event follows a reasonable temporal sequence from the time of drug administration, and/or follows a known response pattern to the study drug, and cannot be reasonably explained by other factors such as the patient's clinical condition, intercurrent illness, or concomitant drugs. |

10.5.5.2 Severity

All TEAEs will be graded for severity. Adverse events will be graded by the Investigator using a numerical score according to the defined National Cancer Institute Common Terminology Criteria for Adverse Events (NCI CTCAE) Version 5.0 (2017). Adverse events not specifically defined in the NCI CTCAE will be scored on the Adverse Event log according to the general guidelines provided by the NCI CTCAE and as outlined in Table 12.

The Investigator will use the terms: Mild, Moderate, Severe, Life Threatening, or Death to describe the maximum intensity of the TEAE. For purposes of consistency, these intensity grades are defined as follows:

| Grade 1 | Mild | Mild; asymptomatic or mild symptoms; clinical or diagnostic observations only; intervention not indicated. |
|---------|---------------------|--|
| Grade 2 | Moderate | Moderate; minimal, local or noninvasive intervention indicated; limiting age-appropriate instrumental ADL ^a |
| Grade 3 | Severe | Severe or medically significant but not immediately life-threatening; hospitalization or prolongation of hospitalization indicated; disabling; limiting self-care ADL ^b |
| Grade 4 | Life threatening | Life-threatening consequences; urgent intervention indicated. |
| Grade 5 | Death | Death related to an adverse event |

Table 12: Guidelines for Severity Assessments

ADL = activities of daily living

a. Instrumental ADL refer to preparing meals, shopping for groceries or clothes, using the telephone, managing money, etc.

b. Self-care ADL refer to bathing, dressing and undressing, feeding self, using the toilet, taking medications, and not bedridden.

10.5.5.3 Serious Adverse Events

Any adverse experience occurring at any dose of study medication that occurs between the time of receiving study medication and within 28 days (\pm 48 hours) in Part 1 or 28 days (\pm 5 days) in Part 2 after administration of study drug that results in any of the following outcomes:

- Death
- Life-threatening situation (patient is at immediate risk of death)
- In-patient hospitalization or prolongation of existing hospitalization
- Persistent or significant disability/incapacity
- Congenital anomaly/birth defect in the offspring of a patient who received study drug
- Events that jeopardize the patient sufficiently that medical or surgical intervention may be required to prevent one of the above outcomes. Examples may include, but are not limited, to:
 - Intensive treatment in an emergency room or at home for allergic bronchospasm
 - Blood dyscrasias that do not result in hospitalization
 - Seizures that do not result in hospitalization

ALL SERIOUS ADVERSE EVENTS MUST BE REPORTED TO THE CONTRACT RESEARCH ORGANIZATION'S DRUG SAFETY DESK WITHIN 24 HOURS USING THE DESIGNATED SERIOUS ADVERSE EVENT REPORTING FORM

10.5.5.3.1 Serious Adverse Event Definition Clarifications

- Death is an outcome of an AE, and not an AE in itself
- All deaths during study drug administration or occurring within 21 (±1) days after administration of study drug, regardless of cause or relationship, must be reported
- "Occurring at any dose" does not imply that the patient is actively receiving study drug at the time of the event
- "Life-threatening" means that the patient was at immediate risk of death from the event as it occurred. This does not include an event that might have led to death, had it occurred with greater severity.
- Complications that occur during hospitalizations are AEs. If an AE prolongs hospitalization, it is an SAE.
- "In-patient hospitalization" means the patient has been formally admitted to a hospital for medical reasons, for any length of time. This may or may not be overnight. It does not include presentation and care within an emergency department (although an emergency department visit may define a medically important event, which is also considered an SAE).
- The Investigator should attempt to establish a diagnosis of the event based on signs, symptoms, and other clinical information. In such cases, the diagnosis should be documented as the TEAE or SAE, rather than as the individual signs or symptoms.

10.5.5.4 Suspected Unexpected Serious Adverse Reactions

Adverse reactions are all untoward and unintended responses to an investigational product related to any dose administered. Unexpected adverse reactions are SUSARs if the following 3 conditions are met:

- 1. The event must be serious (Section 10.5.5.3)
- 2. There must be a certain degree of probability that the event is a harmful and an undesirable reaction to the medicinal product under investigation, regardless of the administered dose
- 3. The adverse reaction must be unexpected, that is to say, the nature and severity of the adverse reaction are not in agreement with the product information as recorded in
 - a. Summary of Product Characteristics for an authorized medicinal product
 - b. Investigator's Brochure

The sponsor or sponsor designee will report SUSARs according to details provided in the study's Safety and Medical Management Plan (or equivalent). The expedited reporting will occur not later than 15 days after the sponsor has first knowledge of the adverse reactions. For fatal or life-threatening cases, the term will be maximal 7 days for a preliminary report with another 8 days for completion of the report.

10.5.6 Dose-limiting toxicity

DLT is defined as any TEAE of Grade 2 or greater that is considered by the Investigator to be possibly related, probably related, or definitively related to ONM-100 treatment (Section 10.5.5.1) and not to surgery, anesthesia, or other study procedures. Toxicity will be graded according to the NCI-Common Terminology Criteria for Adverse Events (CTCAE) (Sibille 2010). TEAEs will be followed closely during the study to identify any potential DLTs. In Part 1, safety results for each cohort will be reviewed by the Internal Safety Review Committee. Escalation to doses higher than those previously tested will not occur until the safety of lower doses has been confirmed following review by the Internal Safety Review.

10.5.7 Adverse Event Follow-up

All unresolved TEAEs ("ongoing" at end of study) will be followed by the study staff until resolution or deemed stable.

For total bilirubin >1.5×ULN on ≥2 consecutive assessments, assess fractionated bilirubin. If liver function tests (ALT, AST, AP, total bilirubin, fractionated bilirubin) show an abnormal elevation (>1.5×ULN), retest weekly until the values have returned to baseline or stabilized.

10.5.8 Adverse Events of Special Interest

There were no TEAEs of special interest in the Phase 1 study (Section 4.2.1.3).

10.5.9 Toxicity Management

The Investigator should employ best medical judgment in determining how to manage TEAEs. Any questions regarding TEAE management should be directed to the Medical Monitor.

10.5.10 Risks for Women of Child-Bearing Potential or During Pregnancy

The risks of ONM-100 administration during pregnancy have not been evaluated. Pregnant and lactating females are excluded from this study.

Male patients and female patients of child-bearing potential (ie, premenopausal women with intact reproductive organs and women <2 years after menopause) must agree to and comply with using medically acceptable contraception including surgical sterilization (eg, hysterectomy, bilateral oophorectomy, bilateral tubal ligation), intrauterine device, oral contraceptive, contraceptive patch, long acting injectable contraceptive, partner's vasectomy, double-barrier method (condom or diaphragm plus spermicide or condom plus diaphragm), or abstinence during the trial and for 6 months thereafter.

Patients must be instructed to inform the Investigator *immediately* if they or their partner become pregnant during the study. Female partners of male patients must complete informed consent to allow the investigator to follow them for the outcome of the pregnancy.

In the event of a confirmed pregnancy, the following actions should be taken:

- Study drug should be discontinued immediately
- The pregnancy should be reported to the Medical Monitor within 24 hours of notification using the applicable Pregnancy Report Form
- The Investigator should counsel the patient regarding the possible effects of prior ONM-100 exposure on the fetus and the need to inform the study site of the outcome of the pregnancy
- The patient must be monitored until the immediate postnatal period or until termination of the pregnancy. The outcome should be reported to the Medical Monitor using the Pregnancy Outcome or Abnormal Pregnancy Outcome form.

Pregnancy is not an AE, in and of itself. However, any pregnancy complication or elective termination of a pregnancy for medical reasons will be recorded as an AE or SAE. A spontaneous abortion is always considered an SAE and will be reported as described in the TEAE and SAE sections. Furthermore, any SAE occurring as an adverse pregnancy outcome poststudy must be reported to the Medical Monitor.

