long acting injectable contraceptive, partner's vasectomy, double-barrier method (condom or diaphragm plus spermicide or condom plus diaphragm), or abstinence during the trial and for 6 months thereafter 6. 7. Adequate potential for follow up 8. Willing and able to provide written informed consent **Exclusion Criteria** Patients must NOT meet any of the following exclusion criteria: 1. Histologically diagnosed by an excisional biopsy procedure 2. **** 3. Life expectancy <12 weeks 4. Karnofsky Performance Status <70% 5. Hepatic impairment (Child-Pugh score >5) or significant liver disease including active hepatitis or cirrhosis 6. Lab values or any sign, symptom, or medical condition that in the opinion of the PI would prevent surgical resection 7. Medical or psychiatric conditions that compromise the patient's ability to give informed consent. 8. Pregnant or lactating women 9. 10. 11. 12. Receiving or planned to receive, during the duration of the study, concomitant medication with a high chance of h 14. Received an investigational agent within the shorter of 5 half-lives or 30 days before ONM-100 dosing 15. Inability to adhere to the schedule of assessments or any circumstance that would interfere with the validity of assessments performed in the study 16. The PI considers that the patient should not participate in the study Test Product, Dose and Mode of Administration

Comparator

There is no comparator imaging agent used in this study.

Expected Duration of Patient Participation

In Part 1, study participation will require 28 days (±48 hours), not counting the prestudy screening visit from Day -30 to Day -1. Following a single dose of ONM-100 administered by IV infusion on Day 0,

are considered clinically significant by the Investigator, will be repeated on Day 28 (±48 days). All TEAEs and abnormal laboratory findings that are considered at least possibly related to ONM-100 will be followed until resolved or stabilized.

In Part 2, study participation will require 28 days (\pm 5 days), not counting the prestudy screening visit from Day -30 to Day -1. Imaging is performed during surgery. Surgery could be on the same day as ONM-100 dosing

abnormal laboratory findings that are considered at least possibly related to ONM-100 will be followed until resolved or stabilized.

In Part 3, study participation will require 28 days (±5 days), not counting the prestudy screening visit from Day -30 to Day -1.

All TEAEs and

All TEAEs and

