7.1 Patient Inclusion Criteria

Patients must meet ALL of the following inclusion criteria to be enrolled:

- 1. Adults ≥ 18 years of age
- 2. Biopsy-confirmed diagnosis for primary or recurrent disease (or high clinical suspicion in the opinion of the Investigator)
 - a. Part 1: Stage 0 to 4
 - b. Part 2:
 - Stage 0 to 4
 - Stage 2 to 4
 - c. Part 3:

Stage 2 to 4

- 3. Acceptable hematologic status (as respective standard surgery protocol requires, as determined by the Investigator), kidney function, and liver function. Elevations of creatinine, ALT, AST, alkaline phosphatase [AP], or total bilirubin ≥1.5× upper limit of normal (ULN) must be determined to be not clinically significant by the Investigator and approved by the Medical Monitor.
- 4. Documented negative serum pregnancy test for women of childbearing potential (ie, premenopausal women with intact reproductive organs and women <2 years after menopause)
- 5. Male patients and female patients of child-bearing potential (ie, premenopausal women with intact reproductive organs and women <2 years after menopause) must agree to and comply with using medically acceptable contraception including surgical sterilization (eg, hysterectomy, bilateral oophorectomy, bilateral tubal ligation), intrauterine device, oral contraceptive, contraceptive patch, long acting injectable contraceptive, partner's vasectomy, double-barrier method (condom or diaphragm plus spermicide or condom plus diaphragm), or abstinence during the trial and for 6 months thereafter.

- 6. Agree to abstain from alcohol consumption
- 7. Adequate potential for follow up

8. Willing and able to provide written informed consent

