9.1.6 Day 3 (±24 hours) (Part 1 only)

• Laboratory assessments

- Obtain blood sample for PK analyses and blood volume (Part 1 & 2 Only)
 - Part 1 (all cohorts): 72 (±24) hours postdose (ie, after infusion has been completed)
- Record all concomitant medications including prescription, OTC, and herbal medications
- Assess, identify, and record any new TEAEs

9.1.7 Day 6 (±24 hours) in Part 1 ;and Day 10 (±5 days) in Part 2 and Part 3

- Clinical assessments
 - Measure vital signs (temperature, heart rate, blood pressure, and respiratory rate)
 - Perform 12-lead ECG
 - Conduct complete physical examination
- Laboratory assessments

• Obtain blood sample for PK analyses and blood volume (Parts 1 & 2)

- Record all concomitant medications including prescription, OTC, and herbal medications
- Assess, identify, and record any new TEAEs

9.1.8 Day 28 (±48 hours) in Part 1; Day 28 (±5 days) in Part 2 and Part 3

Laboratory assessments

- Perform serum pregnancy test on female patients <2 years postmenopausal
- Record all concomitant medications including prescription, OTC, and herbal medications
- Assess, identify, and record any AEs

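### Section 10.5.10 asks patients to report a pregnancy only during the roughly 28-day study, although contraception is required for 6 months beyond it

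*Protocol*

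**What the plan says.** Section 10.5.10 of the protocol opens by stating: "The risks of ONM-100 administration during pregnancy have not been evaluated". It then requires contraception from men and from women who could conceive. The listed methods end with "or abstinence during the trial and for 6 months thereafter", and the same wording stands in inclusion criterion 5 (Section 7.1).

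The next paragraph of Section 10.5.10 deals with notification. Patients must be told to inform the Investigator at once "if they or their partner become pregnant during the study". Once a pregnancy is confirmed, the site reports it to the Medical Monitor within 24 hours on a Pregnancy Report Form, counsels the patient, and follows the pregnancy to its end or to shortly after birth. None of these steps carries a time limit of its own. The section closes by requiring that "any SAE occurring as an adverse pregnancy outcome poststudy must be reported to the Medical Monitor".

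The synopsis gives the length of participation. For Part 1: "In Part 1, study participation will require 28 days (±48 hours), not counting the prestudy screening visit". For Part 3: "In Part 3, study participation will require 28 days (±5 days), not counting the prestudy screening visit". Part 2 has the same length as Part 3. The last scheduled pregnancy test is at the Day 28 visit (Section 9.1.8): "Perform serum pregnancy test on female patients <2 years postmenopausal".

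**The concern.** Every patient receives one dose, so the whole contraception period is time after exposure. The protocol asks patients to avoid conception for six months after the study but, in the text that can be read, does not ask them to say so if avoidance fails in those months.

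This matters because the rest of the pregnancy procedure starts from notification. A conception in the third month would trigger no report, counselling or outcome follow-up unless the site heard of it by chance. For partners of male patients no test is scheduled at any time, so what the patient reports is the main route by which the site would know. The sponsor evidently wants post-study pregnancy safety information, since it asks for serious adverse outcomes after the study. Such outcomes are hard to interpret without knowing how many pregnancies there were. A record with no late pregnancies could not be read with confidence as meaning that none occurred.

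**Working it through.** The plan states no figure for this point, so there is none to reproduce. The check is a ratio of two windows, followed by a reading of whether other text closes the gap.

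**Inputs**
- Participation after dosing: 28 days, with a window of ±48 hours in Part 1 (26 to 30 days) and ±5 days in Parts 2 and 3 (23 to 33 days). Source: synopsis, expected duration of participation.
- Contraception after the trial: 6 months. Source: Sections 7.1 and 10.5.10. Its length in days is my assumption: 182.6 days (half of 365.25), range 180 to 184.
- Notification window: the study itself. The section does not define this in days; I take it to end with participation.

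**Formula**

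Uncovered share = (contraception days after the study) / (participation days + contraception days after the study)

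**Results**

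| Participation (days) | 6 months (days) | Total (days) | Uncovered |
|---|---|---|---|
| 28 | 182.6 | 210.6 | 182.6/210.6 = 86.7% |
| 33 | 180 | 213 | 180/213 = 84.5% |
| 23 | 184 | 207 | 184/207 = 88.9% |
| 30 (Part 1, late) | 180 | 210 | 180/210 = 85.7% |
| 26 (Part 1, early) | 184 | 210 | 184/210 = 87.6% |

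The instruction covers 28/210.6 = 13.3% of the period in the central case.

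**Can the notification window be read as including the 6 months?** Not naturally. The contraception rule separates the trial from the months that follow it, and the closing sentence of Section 10.5.10 separates the study from what comes after it.

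**Does other visible text close the gap?**
- Section 9.1.8 lists laboratory work, the pregnancy test, concomitant medication and adverse events for Day 28. It says nothing about later pregnancies.
- No contact is scheduled after Day 28. Section 10.5.7 continues follow-up only for unresolved adverse events.
- Section 10.5.5.3 counts a congenital anomaly as a serious outcome but ties serious events to 28 days after dosing. A child conceived after dosing would not be born within that time, so this outcome depends on knowing of the pregnancy.
- The confirmed-pregnancy steps and the post-study rule in Section 10.5.10 would apply to a late pregnancy, but each begins only when the site knows of it.

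**The case against.** The strongest objection is that the places where a longer instruction would naturally stand cannot be seen. The list under Section 9.1.1 (Patient Restrictions) is blank, the footnotes to the pregnancy-test rows of the schedule tables are missing, and the consent pages were removed. This stands as a limit on certainty. A reader might infer that nobody will be asked about later pregnancies; the documents do not support that, because the claim holds only for the visible text. The objection does not remove the point, though. A longer instruction elsewhere would disagree with Section 10.5.10 and would still need reconciling.

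Second, how long contraception lasts and how long pregnancies are notified are separate rules, so the mismatch is not a contradiction in the strict sense. That is fair. The protocol also never calls the 6 months a period of risk; that is an inference from the contraception requirement.

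Third, Section 10.5.10 does give cover after the study. Its confirmed-pregnancy steps are untimed, a spontaneous abortion always counts as serious, and serious adverse pregnancy outcomes after the study must be reported. A reader might infer that the post-study rule cannot work at all. That goes too far: a site may learn of a pregnancy in routine oncology follow-up. What is missing is narrower, namely the instruction to the patient.

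Fourth, a reader might add that a conception shortly before Day 28 could escape the Day 28 test and so widen the gap. It does not. Such a pregnancy arose during the study, and the existing instruction already covers it whatever the test shows.

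Fifth, the percentage counts calendar days, not risk. Enrolment is capped at 60, those who could conceive must use contraception, and no objective concerns reproductive safety. All of this stands and limits the weight of the point.

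**Conclusion.** The point holds in a limited form. The notification rule in Section 10.5.10 is stated, but it is narrower than the contraception rule in the same section. About 87% of the contraception period after dosing, and 85% to 89% across the permitted visit windows, has no visible instruction to notify.

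The conclusion rests on three assumptions: that the study, for this sentence, ends with participation at about Day 28; that 6 months is 180 to 184 days; and that no longer instruction stands in the redacted or removed text.

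The figure is a share of time. It should not be read as a share of risk or as a forecast of missed pregnancies. The documents give no pregnancy rate, and with at most 60 patients under a contraception requirement I would expect few events. Efficacy results are unaffected. This is a worthwhile correction to safety follow-up, not a defect that threatens the trial's conclusions.

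**What to change.** First check the unredacted Patient Restrictions list, the footnotes to the schedule tables and the consent form. If any of them already sets a longer notification period, bring Section 10.5.10 into line with it and with the contraception period.

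Otherwise, change three things:
- In Section 10.5.10, extend the notification sentence to a pregnancy of the patient or partner that arises during the study or within the 6-month contraception period defined in inclusion criterion 5.
- State that the existing Pregnancy Report Form, its 24-hour deadline and the existing outcome follow-up apply to those reports.
- Repeat the instruction to the patient in the Day 28 visit procedures (Section 9.1.8) and in the consent form.

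No visit or test is added. The cost is a sentence in each place and a safety contact that stays open for about 6 months after each patient's last visit. Follow-up can run longer than that: a pregnancy notified late in the period must be followed until shortly after birth, and a partner's pregnancy needs her own consent. With few events expected, this burden should be small.
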